8.9 Long Term Follow-Up Evaluations (\pm 2weeks)

Participants will be monitored every 3 months for up to 4 years (telephone contact is acceptable). Monitoring will be performed to assess further therapies administered and survival.

Participants who are unavailable for follow-up evaluations should be classified as lost to follow-up for 1 of the following reasons:

- Lost to follow-up: For a participant to be considered lost to follow-up, the investigator must make two separate attempts to re-establish contact with the participant. The attempts to re-establish participant contact must be documented (e.g., certified letter).
- Death: Date and cause of death will be recorded for those participants who die within 30 days after last dose of study drug (telephone verification is acceptable).

8.10 Second Course Phase (Retreatment Period)

Participants who stop cetuximab and pembrolizumab with SD or better may be eligible for up to one year of additional therapy if they progress after stopping study treatment. This retreatment is termed the Second Course Phase of this study and is only available if the study remains open and the subject meets the following conditions:

- **Either**

- Stopped initial treatment with pembrolizumab after attaining an investigator-determined confirmed CR according to RECIST 1.1, and
 - Was treated for at least 24 weeks with pembrolizumab before discontinuing therapy
 - Received at least two treatments with pembrolizumab beyond the date when the initial CR was declared

OR

- Had SD, PR or CR and stopped pembrolizumab treatment after 24 months of study therapy for reasons other than disease progression or intolerability

AND

- Experienced an investigator-determined confirmed radiographic disease progression after stopping their initial treatment with pembrolizumab
- Did not receive any anti-cancer treatment since the last dose of pembrolizumab
- Has a performance status of 0 to 2 on the ECOG Performance Scale (**Appendix B**)
- Meets the safety parameters as detailed in **Section 5.1**
- Female participants of childbearing potential should have a negative serum or urine pregnancy test within 72 hours prior to receiving retreatment with study medication.
- Female participants of childbearing potential should be willing to use 2 methods of birth control or be surgically sterile, or abstain from heterosexual activity for the course of the study through 120 days after the last dose of pembrolizumab and 180 days after the last dose of cetuximab. (Reference **Section 5.1**). Participants of child bearing potential are those who have not been surgically sterilized or have been free from menses for > 1 year.
- Does not have a history or current evidence of any condition, therapy, or laboratory abnormality that might interfere with the participant's participation for the full duration of the trial or is not in the best interest of the participant to participate, in the opinion of the treating investigator.

Participants who restart treatment will be retreated at the same dose and dose interval as when they last received cetuximab and pembrolizumab. Treatment will be administered for up to one additional year.

Visit requirements are outlined in **5: Schedule of Procedures and Observations for Second Treatment Course**. Both cetuximab and pembrolizumab would restart simultaneously.

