			participants with liver metastases	
			9. Female participants of childbearing potential are to have a negative serum pregnancy test.	
			10. Female participants of child-bearing potential must agree to use an acceptable method of birth control, be surgically sterile, or abstain from heterosexual activity for the course of the study through 120 days after the last dose of pembrolizumab and 180 days after the last dose of cetuximab. Participants of childbearing potential are those who have not been surgically sterilized or have not been free from menses for > 1 year. Should a woman become pregnant or suspect she is pregnant while she or her partner is participating in this study, she should inform her treating physician immediately	
			11. Male participants must agree to use an adequate method of contraception starting with the first dose of study therapy through 120 days after the last dose of pembrolizumab and 180 days after the last dose of cetuximab	
			12. Participant or legal representative must understand the investigational nature of this study and sign an Independent Ethics Committee/Institutional Review Board approved written informed consent form prior to receiving any study related procedure.	

Investigator Signature: _____

Date: _____

Printed Name of Investigator: _____

INVESTIGATOR STUDY ELIGIBILITY VERIFICATION FORM

Participant Name: (Network sites use participant initials): _____

Medical Record No.: (Network sites use participant ID): _____

Title: A Phase II Study of Cetuximab and Pembrolizumab in Metastatic Colorectal Cancer.

EXCLUSION CRITERIA				
Yes	No	N/A	All answers must be "No" or "N/A" for participant enrollment.	Date
			1. Participants who have had chemotherapy, targeted therapies, radiotherapy, or used an investigational device within 2 weeks prior to the first dose of treatment or those who have not recovered from adverse events (i.e., \leq Grade 1 or at baseline) due to agents administered more than 2 weeks earlier. Note: Participants with \leq Grade 2 neuropathy are an exception to this criterion and may qualify for the study	

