6.3.14 Diet/Activity/Other Considerations

Diet

Participants should maintain a normal diet unless modifications are required to manage an AE such as diarrhea, nausea or vomiting.

Contraception

Pembrolizumab may have adverse effects on a fetus in utero. Furthermore, it is not known if pembrolizumab has transient adverse effects on the composition of sperm. Non-pregnant, non-breast-feeding women may be enrolled if they are willing to use 2 methods of birth control or are considered highly unlikely to conceive. Highly unlikely to conceive is defined as 1) surgically sterilized, or 2) postmenopausal (a woman who is ≥ 45 years of age and has not had menses for greater than 1 year will be considered postmenopausal), or 3) not heterosexually active for the duration of the study. The two birth control methods can be: two barrier methods or, a barrier method plus a hormonal method, to prevent pregnancy. Participants should start using birth control from study Visit 1 (prescreening visit) throughout the study period up to 120 days after the last dose of pembrolizumab and 180 days after the last dose of cetuximab.

The following are considered adequate barrier methods of contraception: diaphragm, condom (by the partner), copper intrauterine device, sponge, or spermicide. Appropriate hormonal contraceptives will include any registered and marketed contraceptive agent that contains an estrogen and/or a progestational agent (including oral, subcutaneous, intrauterine, or intramuscular agents).

Participants should be informed that taking the study medication may involve unknown risks to the fetus (unborn baby) if pregnancy were to occur during the study. In order to participate in the study they must adhere to the contraception requirement (described above) for the duration of the study and during the follow-up period defined in **Section 8**. If there is any question that a participant will not reliably comply with the requirements for contraception, that participant should not be entered into the study.

Use in Pregnancy

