
Evaluation	Baseline¹	Cycle 1 Day 1 (± 3 days)	Cycle 1 Day 8 (± 3 days)	Cycle 1 Day 15 (± 3 days)	Further Cycles Day 1 (± 3 days)	Further Cycles Days 8, 15 (± 3.days)	Cycle 4 Day 1 (± 3 days)	Off Treatment Visit	Safety² Follow-Up	Safety¹⁹ Follow-up #2	Long Term Follow-Up³

18 For completion of MSI testing, when necessary, peripheral blood may need to be drawn, depending upon the sample which is able to be tested. Any time point within the 1st 4 weeks on treatment is acceptable, though request at baseline is preferred.
 
19 Second follow-up safety eval, labs only, to occur 60 days(± 7 days) after last dose of study drug.
 
20 Serum pregnancy test to be performed once every 6 months on women of childbearing potential only – cycle 9, 17, 25, etc...
 
21 Consent addendum should be obtained to continue on treatment past progression. See section 6.5
											

Table 5 Second Course Phase Treatment Schedule

Evaluation	Cycle 1 Day 1	Cycle 1 Day 8, 15 (± 3 days)	Further Cycles Day 1 (± 3 days)	Further Cycles Days 8, 15 (± 3.days)	Off Treatment Visit	Safety ² Follow-Up	Safety Follow-up #2 ¹³	Long Term Follow-Up ³
Eligibility criteria ¹	X							
Physical Examination	X		X		X	X		
Vital signs ⁴	X	X	X	X	X	X		
ECOG PS					X			
Hematology ⁵	X		X		X	X		
BMP (with Mg) ⁶		X		X				
CMP (with Mg) ⁷	X		X		X	X	X	
CEA	X		X					
Pregnancy Test (Serum) ⁸	X		X ¹⁴					
TSH, total T3, Free T4	X ¹²		X ¹²		X	X		
Tumor Imaging (CT/MRI) ⁹	X ¹⁰							
Pembrolizumab	X		X					
Cetuximab	X	X	X	X				
Concomitant Medications ¹¹	X		X		X	X		
Adverse Events	X		X		X	X		
Post Therapy Status								X

1 Performed within 2 weeks prior to treatment start.

2 Follow-up safety evaluations will occur 30 days (± 7 days) after last dose of study drug. SAEs to be reported for up until 90 days after last study treatment.

3 Participants will be monitored for survival, further treatments every 3 months for up to 4 years (telephone contact is acceptable).

Evaluation	Cycle 1 Day 1	Cycle 1 Day 8, 15 (± 3 days)	Further Cycles Day 1 (± 3 days)	Further Cycles Days 8, 15 (± 3.days)	Off Treatment Visit	Safety ² Follow-Up	Safety Follow-up #2 ¹³	Long Term Follow-Up ³
4	Vital signs: temperature, heart rate, respiratory rate, blood pressure, and body weight. Height collected at baseline only.							

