5	Hematology (CBC with automated differentials): WBC, RBC, HGB, HCT, platelet, MCV, MCH, MCHC, % neutrophils, absolute neutrophils, % monocytes, absolute monocytes, % eosinophils, absolute eosinophils, % basophils, absolute basophils, % lymphocyte total, absolute lymphocyte total, platelet confirmation (as clinically indicated), and differential confirmation (as clinically indicated).							
6	Basic Metabolic Panel (BMP) with magnesium: chloride, CO ₂ , potassium, sodium, BUN, glucose, calcium, creatinine, magnesium							
7	Complete Metabolic Panel (CMP): chloride, CO ₂ , potassium, sodium, BUN, glucose, calcium, creatinine, total protein, albumin, total bilirubin, alkaline phosphatase, AST, ALT, A/G ratio, BUN/creatinine ratio, osmol (Calc), anion gap), direct bilirubin (if total bilirubin is elevated above the upper limit of normal), magnesium.							
8	Perform on women of childbearing potential only. within 2 weeks prior to start of treatment.							
9	CT preferred, though Non-contrast CT chest and MRI abd/pelvis is an acceptable alternative if a contrast enhanced CT cannot be performed. Restaging will be performed every 9 weeks (+/- 7 days from Cycle 1 day 1).							
10	Imaging for cycle 1 day 1 of retreatment can be performed up to 28 days prior to cycle 1 day 1/							
11	Medications ongoing, or discontinued, within 1 week prior to first dose of study drug.							
12	TFTs (TSH, Total T3, Free T4 to be drawn on day 1 every other cycle beginning with cycle 1, i.e. cycle 1, 3, 5, 7, etc...)							
13	Second follow-up safety eval, labs only, to occur 60 days(± 7 days) after last dose of study drug.							
14	Serum pregnancy test to be performed once every 6 months on women of childbearing potential only – cycle 9, 17, 25, etc...							

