3. PARTICIPANT REGISTRATION

The participant completes the Gender, Race, and Ethnicity Form and this is placed in the study binder.

RPCI does not grant exceptions to eligibility criteria.

Phase 1 Protocol Registration Instructions

Contact the RPCI Network Monitor to verify that a slot is available in the open cohort when a participant has been identified. **Do not have the participant sign consent prior to verifying an open slot.**

- After the participant signs consent, the Subject Screening and Enrollment Log must be faxed or emailed to the RPCI Network Monitor within 1 business day. The RPCI Network Monitor

will confirm receipt of the Subject Screening and Enrollment Log and email the participant ID number.

- When the participant has met eligibility, a signed eligibility checklist and other requested documentation will be faxed or emailed to the RPCI Network Monitor.
- Within 1 business day of receipt of the eligibility check list, the RPCI Network Monitor will fax or email the cohort assignment and dose level.
- An email must be sent by the site to confirm receipt of the cohort assignment and to provide the planned treatment start date.

Phase 2 Protocol Registration Instructions

The Subject Screening and Enrollment Log must be faxed or emailed to the RPCI Network Office within 1 business day of the date the participant is consented. Once the Investigator has determined that eligibility has been met, complete the eligibility check list and fax or email it to the RPCI Network Monitor at [contact].

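### Table 5 lets retreatment start on a pregnancy test up to 2 weeks old, although section 8.10 requires one within 72 hours; contraception and pregnancy-reporting wording also needs aligning

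*Combined protocol and SAP*

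**What the plan says.** **Retreatment test.** Section 8.10 lists the conditions for entering the Second Course Phase. One is that women of childbearing potential "should have a negative serum or urine pregnancy test within 72 hours prior to receiving retreatment with study medication". The section then sends sites to item 5, the "Schedule of Procedures and Observations for Second Treatment Course", for visit requirements; section 8.11 identifies this as Table 5. The pregnancy row of Table 5 is labelled serum, and note 8 sets its timing as "within 2 weeks prior to start of treatment".

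**Tests at other times.** Table 4 note 20 reads "Serum pregnancy test to be performed once every 6 months on women of childbearing potential only" and names cycles 9, 17 and 25. Sections 8.6 to 8.9 (off-treatment visit, both safety follow-ups, long-term follow-up) list no pregnancy test.

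**Contraceptive methods.** Section 5.1 item 11 and item 10 of the eligibility checklist say that women of childbearing potential "must agree to use an acceptable method of birth control, be surgically sterile, or abstain from heterosexual activity". Section 6.3.14 says that women "may be enrolled if they are willing to use 2 methods of birth control or are considered highly unlikely to conceive". Section 8.10 says that they "should be willing to use 2 methods of birth control or be surgically sterile", or abstain, and cites section 5.1.

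**Pregnancy reporting.** Contraception runs to 120 days after the last pembrolizumab dose and 180 days after the last cetuximab dose. Section 10.4.1 sets reporting to 120 days after completing the trial, or to 30 days after treatment cessation if new anticancer therapy starts, whichever comes first.

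**The concern.** The schedule table is what site staff use to book procedures. Here it is looser than the condition it is meant to carry out, and the error runs in the unsafe direction: both antibodies could be restarted in a woman whose pregnancy a more recent test would have shown.

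The retreatment test carries real weight. No test is scheduled in the treatment-free interval, and the first-course contraception duty ends 120 and 180 days after the last doses. Section 8.10 sets no limit on how long after stopping a woman may re-enter, so retreatment can begin after that duty has lapsed.

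The contraception wording matters because of how registration works. Appendix A tells network sites: "Once the Investigator has determined that eligibility has been met, complete the eligibility check list" and send it in. No item on that form states the two-method rule. The reporting wording matters because information on a late exposure could be lost within a period that the protocol itself treats as one of risk.

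**Working it through.** No plan figure needs reproducing; the check is a comparison of texts plus day counts.

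**1. Retreatment test**

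| Test before first retreatment dose | Section 8.10 | Table 5, note 8 |
|---|---|---|
| Serum, 0 to 3 days old | meets | meets |
| Urine, 0 to 3 days old | meets | does not meet (serum row) |
| Serum, 4 to 14 days old | breaches | meets |
| More than 14 days old | breaches | breaches |

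The range accepted only by Table 5 is 14 − 3 = 11 days (336 − 72 = 264 hours). Table 5 also has an eligibility row at Cycle 1 Day 1, but its note 1 likewise allows 2 weeks, so it does not bring in the 72-hour limit. Two weeks is also the first-course baseline window (Table 4 note 1), which may be where note 8 came from.

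**2. Age of the last on-treatment test**

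Day 1 of cycle c falls (c − 1) × 21 days after first dose: cycle 9 = day 168, cycle 17 = day 336, cycle 25 = day 504. Tests are 8 × 21 = 168 days apart. With none scheduled after treatment ends, the last one before retreatment can be up to about 168 days old at the end of treatment, plus the whole treatment-free interval.

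**3. Contraceptive methods**

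Section 6.3.14 makes two methods, or being highly unlikely to conceive, a condition of enrolment. Section 8.10 asks for two and points to section 5.1, but section 5.1 does not say two. The definitions differ as well:
- Section 5.1 uses more than 1 year without menses, with no age limit.
- Section 6.3.14 adds age 45 or over for postmenopausal status.
- Section 8.10 drops the second *not* from the section 5.1 definition, so that, read literally, a woman free from menses for over a year counts as of childbearing potential.

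**4. Reporting window**

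Take both drugs stopping on the same day (day 0).
- New therapy started by day 30: reporting ends at day 30. The gap is 180 − 30 = 150 days to the cetuximab limit and 120 − 30 = 90 days to the pembrolizumab limit.
- No new therapy, trial completion read as last dose: 180 − 120 = 60 days.
- No new therapy, trial completion read as the end of long-term follow-up (up to 4 years in section 8.9): no gap.

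The documents do not define trial completion.

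**The case against.** **Retreatment test.** Section 8.10 remains a condition of retreatment, and a serum test within 72 hours satisfies both texts, so a careful site can comply with everything. That stands. A reader might infer that the protocol permits retreatment on a two-week-old test; it does not, because Table 5 does not cancel section 8.10. The word *should* in section 8.10 does not help Table 5, since the sentence sits in a list of required conditions.

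A reader might also infer that women commonly re-enter with only a baseline test behind them. The documents do not support that. The complete-response route needs at least 24 weeks of pembrolizumab, and 24 weeks is day 168, when the cycle 9 test falls due. Only a woman stopping right at that boundary would miss it. On the 24-month route, the tests at cycles 9, 17 and 25 have fallen due.

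**Methods.** A reader might infer that section 5.1 accepts a single method. It does not say that one is enough. Section 6.3.14 makes adherence a requirement for participation, and Exclusion 17, which is on the checklist, covers unwillingness to follow protocol requirements. The rule already binds sites; the defect is that section 5.1 and the form do not show it.

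**Reporting.** The 30-day cut on new therapy matches the SAE and ECI rules in sections 10.2.2 and 10.4.1 and may be a deliberate convention. A reader might infer that late pregnancies go unreported. That is too strong:
- Section 10.4.1 requires pregnancies to be followed to their end and losses to be reported as serious.
- Section 10.2.2 covers drug-related SAEs at any time.
- Section 6.3.14 asks for partner pregnancies to be reported, with no time limit of its own, though it also refers to section 10.4.1.

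What remains is that no text clearly requires every pregnancy late in the window to be reported as such.

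**Conclusion.** The retreatment-test conflict is real and should be corrected. For 11 of the 14 days that Table 5 allows, a test meets the schedule but breaches section 8.10, and no test is scheduled between the end of treatment and re-entry. The number of women affected is likely to be very small. At most 42 participants enrol, and re-entry needs either a confirmed complete response after at least 24 weeks or 24 months of therapy, followed by progression with no other treatment. The documents give no count of women of childbearing potential.

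The two-method mismatch is a secondary inconsistency: the rule is in force but missing from section 5.1 and the checklist.

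The reporting point is minor. Its 150 days assume that both drugs stop together and that new therapy starts by day 30. Without new therapy the gap is 60 days or none, depending on an undefined phrase.

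All three are matters of patient safety and document consistency. None touches efficacy, power or type I error.

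**What to change.** 1. **Table 5, note 8:** require the test within 72 hours before the first retreatment dose, and name one sample type in both Table 5 and section 8.10. Serum is the smaller edit, since section 5.1 item 10 and both schedules already use it.
2. **Section 5.1 item 11 and checklist item 10:** state the two-method rule with its exceptions, so that the section 8.10 reference to section 5.1 is correct. Choose one definition of childbearing potential for sections 5.1, 6.3.14 and 8.10. Copying section 6.3.14 unedited would bring its age-45 criterion into conflict with section 5.1.
3. **Section 10.4.1:** replace *completing the trial* with last-dose dates. Consider extending reporting to the later of 120 days after pembrolizumab and 180 days after cetuximab, whether or not new therapy starts. If the 30-day cut is kept, say that it is intended.

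The cost is wording in these sections, the checklist and one table note. In practice it means an occasional retest when a retreatment sample is more than 72 hours old and, if item 3 is extended, a little more pregnancy follow-up. Sample size, scheduled visits and analyses do not change.

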8.11 Schedule of Procedures and Observations

The schedule of procedures and observations for this study is summarized in **Table 4 below**.

The Second Course Phase Treatment Schedule of procedure and observations for this study is summarized in table 5 below.

Table 4 Schedule of Procedures and Observations

Evaluation	Baseline¹	Cycle 1 Day 1 (± 3 days)	Cycle 1 Day 8 (± 3 days)	Cycle 1 Day 15 (± 3 days)	Further Cycles Day 1 (± 3 days)	Further Cycles Days 8, 15 (± 3 days)	Cycle 4 Day 1 (± 3 days)	Off Treatment Visit	Safety² Follow-Up	Safety¹⁹ Follow-up #2	Long Term Follow-Up³
Medical History	X										
Physical Examination⁴	X	X			X		X	X	X		
Vital signs⁵	X	X	X	X	X	X	X	X	X		
Directed Physical Exam				X							
ECOG PS	X							X			
Hematology⁶	X	X			X		X	X	X		
BMP (with Mg)⁷			X	X		X					
CMP (with Mg)⁸	X	X			X		X	X	X	X ¹⁹	
CEA		X			X		X				
Urinalysis⁹	X										
Pregnancy Test (Serum)¹⁰	X						X ²⁰				
TSH, total T3, Free T4	X				X ¹⁴		X	X	X		
Tumor Imaging (CT/MRI)¹¹	X						X ²¹				
Biomarker Analysis Blood Draw¹²		X			X ¹²		X				
Tumor Biopsy	X ¹⁶						X ¹⁵				
MMR Documentation/ Testing¹⁷	X										
Blood draw for MSI¹⁸	X										
Pembrolizumab		X			X		X				
Cetuximab		X	X	X	X	X	X				

Evaluation	Baseline ¹	Cycle 1 Day 1 (± 3 days)	Cycle 1 Day 8 (± 3 days)	Cycle 1 Day 15 (± 3 days)	Further Cycles Day 1 (± 3 days)	Further Cycles Days 8, 15 (± 3 days)	Cycle 4 Day 1 (± 3 days)	Off Treatment Visit	Safety ² Follow-Up	Safety ¹⁹ Follow-up #2	Long Term Follow-Up ³
Concomitant Medications	X ¹³	X		X	X		X	X	X		
Adverse Events	X	X		X	X		X	X	X		
Post anti-Cancer Therapy Status											X

 1 Performed within 2 weeks prior to treatment start. 2 Follow-up safety evaluations will occur 30 days (± 7 days) after last dose of study drug. SAEs to be reported for up until 90 days after last study treatment. 3 Participants will be monitored for survival, further treatments every 3 months for up to 2 years (telephone contact is acceptable). (± 2 weeks) 4 Standard of care physical exam may be used if performed within 2 weeks prior to signed consent. 5 Vital signs: temperature, heart rate, respiratory rate, blood pressure, and body weight. Height collected at baseline only. 6 Hematology (CBC with automated differentials): WBC, RBC, HGB, HCT, platelet, MCV, MCH, MCHC, % neutrophils, absolute neutrophils, % monocytes, absolute monocytes, % eosinophils, absolute eosinophils, % basophils, absolute basophils, % lymphocyte total, absolute lymphocyte total, platelet confirmation (as clinically indicated), and differential confirmation (as clinically indicated). 7 Basic Metabolic Panel (BMP) with magnesium: chloride, CO₂, potassium, sodium, BUN, glucose, calcium, creatinine, magnesium 8 Complete Metabolic Panel (CMP): chloride, CO₂, potassium, sodium, BUN, glucose, calcium, creatinine, total protein, albumin, total bilirubin, alkaline phosphatase, AST, ALT, A/G ratio, BUN/creatinine ratio, osmol (Calc), anion gap), direct bilirubin (if total bilirubin is elevated above the upper limit of normal), magnesium. 9 Microscopic exam if results are abnormal. 10 Perform on women of childbearing potential only. 11 Baseline imaging with 30 days prior to the first dose of study drug is acceptable. CT preferred, though Non-contrast CT chest and MRI abd/pelvis is an acceptable alternative if a contrast enhanced CT cannot be performed. Restaging will be performed every 9 weeks (+/- 7 days from Cycle 1 day 1) 12 Blood draws for biomarker analysis will be collected according to Section 8.12. To be performed Cycle 1 day 1, Cycle 2 day 1, Cycle 4 day 1. All are drawn pre-dose. 13 Medications ongoing, or discontinued, within 1 week prior to first dose of study drug. 14 TFTs (TSH, Total T3, Free T4 to be drawn on day 1 every other cycle beginning with cycle 2, i.e. cycle 2, 4, 6, 8, etc...) 15 Tumor Biopsy – cycle 4 Day 1, +/- 7 days 16 Please refer to Section 8.12.1 and Section 8.12.2 17 Mismatch repair protein (MMR) testing (for proteins: MLH1, MSH2, MSH6, PMS2) and/or microsatellite instability(MSI) testing results must be documented. Either is sufficient. If neither is available, testing is to be requested for at least one of these, as per the institution standard. 											

Evaluation	Baseline¹	Cycle 1 Day 1 (± 3 days)	Cycle 1 Day 8 (± 3 days)	Cycle 1 Day 15 (± 3 days)	Further Cycles Day 1 (± 3 days)	Further Cycles Days 8, 15 (± 3.days)	Cycle 4 Day 1 (± 3 days)	Off Treatment Visit	Safety² Follow-Up	Safety¹⁹ Follow-up #2	Long Term Follow-Up³

18 For completion of MSI testing, when necessary, peripheral blood may need to be drawn, depending upon the sample which is able to be tested. Any time point within the 1st 4 weeks on treatment is acceptable, though request at baseline is preferred.
 
19 Second follow-up safety eval, labs only, to occur 60 days(± 7 days) after last dose of study drug.
 
20 Serum pregnancy test to be performed once every 6 months on women of childbearing potential only – cycle 9, 17, 25, etc...
 
21 Consent addendum should be obtained to continue on treatment past progression. See section 6.5
											

Table 5 Second Course Phase Treatment Schedule

Evaluation	Cycle 1 Day 1	Cycle 1 Day 8, 15 (± 3 days)	Further Cycles Day 1 (± 3 days)	Further Cycles Days 8, 15 (± 3.days)	Off Treatment Visit	Safety ² Follow-Up	Safety Follow-up #2 ¹³	Long Term Follow-Up ³
Eligibility criteria ¹	X							
Physical Examination	X		X		X	X		
Vital signs ⁴	X	X	X	X	X	X		
ECOG PS					X			
Hematology ⁵	X		X		X	X		
BMP (with Mg) ⁶		X		X				
CMP (with Mg) ⁷	X		X		X	X	X	
CEA	X		X					
Pregnancy Test (Serum) ⁸	X		X ¹⁴					
TSH, total T3, Free T4	X ¹²		X ¹²		X	X		
Tumor Imaging (CT/MRI) ⁹	X ¹⁰							
Pembrolizumab	X		X					
Cetuximab	X	X	X	X				
Concomitant Medications ¹¹	X		X		X	X		
Adverse Events	X		X		X	X		
Post Therapy Status								X

1 Performed within 2 weeks prior to treatment start.

2 Follow-up safety evaluations will occur 30 days (± 7 days) after last dose of study drug. SAEs to be reported for up until 90 days after last study treatment.

3 Participants will be monitored for survival, further treatments every 3 months for up to 4 years (telephone contact is acceptable).

Evaluation	Cycle 1 Day 1	Cycle 1 Day 8, 15 (± 3 days)	Further Cycles Day 1 (± 3 days)	Further Cycles Days 8, 15 (± 3.days)	Off Treatment Visit	Safety ² Follow-Up	Safety Follow-up #2 ¹³	Long Term Follow-Up ³
4	Vital signs: temperature, heart rate, respiratory rate, blood pressure, and body weight. Height collected at baseline only.							
5	Hematology (CBC with automated differentials): WBC, RBC, HGB, HCT, platelet, MCV, MCH, MCHC, % neutrophils, absolute neutrophils, % monocytes, absolute monocytes, % eosinophils, absolute eosinophils, % basophils, absolute basophils, % lymphocyte total, absolute lymphocyte total, platelet confirmation (as clinically indicated), and differential confirmation (as clinically indicated).							
6	Basic Metabolic Panel (BMP) with magnesium: chloride, CO ₂ , potassium, sodium, BUN, glucose, calcium, creatinine, magnesium							
7	Complete Metabolic Panel (CMP): chloride, CO ₂ , potassium, sodium, BUN, glucose, calcium, creatinine, total protein, albumin, total bilirubin, alkaline phosphatase, AST, ALT, A/G ratio, BUN/creatinine ratio, osmol (Calc), anion gap), direct bilirubin (if total bilirubin is elevated above the upper limit of normal), magnesium.							
8	Perform on women of childbearing potential only. within 2 weeks prior to start of treatment.							
9	CT preferred, though Non-contrast CT chest and MRI abd/pelvis is an acceptable alternative if a contrast enhanced CT cannot be performed. Restaging will be performed every 9 weeks (+/- 7 days from Cycle 1 day 1).							
10	Imaging for cycle 1 day 1 of retreatment can be performed up to 28 days prior to cycle 1 day 1/							
11	Medications ongoing, or discontinued, within 1 week prior to first dose of study drug.							
12	TFTs (TSH, Total T3, Free T4 to be drawn on day 1 every other cycle beginning with cycle 1, i.e. cycle 1, 3, 5, 7, etc...)							
13	Second follow-up safety eval, labs only, to occur 60 days(± 7 days) after last dose of study drug.							
14	Serum pregnancy test to be performed once every 6 months on women of childbearing potential only – cycle 9, 17, 25, etc...							

